1. INTRODUCTION

This statistical analysis plan (SAP) describes the statistical methods to be used for analyses and data presentation for reporting efficacy and safety results for study ALK3831-401. This document has been prepared based on Alkermes [ALK3831-401 Study Protocol Amendment 6¹](#) (dated 01 Mar 2016).

1.1. Study Objectives

Primary:

- To evaluate the efficacy of olanzapine coadministered with samidorphan (ALKS 3831) compared with olanzapine coadministered with placebo in schizophrenia with alcohol use disorder (AUD)

Secondary:

- To evaluate the safety and tolerability of ALKS 3831 in schizophrenia with AUD

1.2. Summary of the Study Design

This is a Phase 2, multicenter, randomized, double-blind, placebo-controlled study designed to evaluate the efficacy, safety, and tolerability of ALKS 3831 in schizophrenia with AUD.

ALKS 3831 is a combination of olanzapine, an approved antipsychotic treatment for schizophrenia, and samidorphan, a new molecular entity.

Potential subjects for this study are adults with a diagnosis of schizophrenia (based on the Diagnostic and Statistical Manual of Mental Disorders 4th edition, text revision [DSM-IV-TR]) and AUD (based on DSM 5th edition [DSM-5]). Subjects must have recently (within the last 6 months) experienced an exacerbation of disease symptoms (eg, hospitalization) but cannot exceed a pre-defined level of symptom severity at the time of screening (as measured by the Positive and Negative Syndrome Scale [PANSS] and Clinical Global Impression-Severity [CGI-S]).

[figure not shown]
All study visits will be outpatient visits. After informed consent and screening, subjects will begin a 4-week open-label olanzapine dosing period followed by a 2-week open-label ALKS 3831 period (see [Figure 1](#)). Once-daily, open-label olanzapine dosing will begin at Visit 2 with the dose level determined by the principal investigator (PI). Once daily open-label ALKS 3831 dosing (olanzapine coadministered with 10 mg samidorphan using separate tablets) will begin at Visit 6 and last until Visit 8 (randomization). ALKS 3831 treatment will consist of a once-daily dose of olanzapine (with dose level determined by the PI) plus samidorphan 10 mg to be taken at the same time (ie, coadministered) using separate tablets.

At Visit 8, subjects will be randomized in a 1:1 fashion to 1 of 2 treatment groups as follows:

- ALKS 3831 (ie, olanzapine [dose determined by the PI] plus samidorphan [10 mg])
- Olanzapine (dose determined by the PI) plus placebo

Subjects randomized to double-blind treatment will be followed for a minimum of 9 months and a maximum of 15 months. Visits during the double-blind period will be every 2 weeks. Each visit will consist of clinical assessments plus drug dispensing or drug dispensing only. After the end of the double-blind treatment period, subjects will complete a 3-week safety follow-up period.

Figure 1: ALK3831-401 Study Schematic

Abbreviation: V = Study Visit; ALKS 3831=olanzapine + samidorphan

The schedule of visits and assessments for before randomization (Visit 8) and after randomization are shown in [Table 1](#), [Table 2](#), and [Table 3](#) of the protocol ([Study ALK3831-401¹](#)).

2. SAMPLE SIZE CONSIDERATION

The sample size calculation is based on the detection of hazard ratio for the first event of exacerbation of disease symptoms (EEDS) during the double-blind treatment period.

Based on the previous clinical studies with olanzapine and clinical judgment, the 9-month cumulative proportion of subjects experiencing an event of exacerbation of disease symptoms (EEDS) will be 15% and 30% for the ALKS 3831 group and olanzapine plus placebo group, respectively. Assuming an exponential distribution of survival time, and a 2-sided test at $\alpha=0.05$, a total of 70 EEDS will be required for approximately 90% power to detect a hazard ratio of 0.45 between ALKS 3831 and olanzapine plus placebo with a randomization allocation ratio of 1:1 (ALKS 3831:olanzapine plus placebo). Approximately 270 subjects (135 subjects per treatment group) will need to be randomized at Visit 8 to observe 70 total EEDS.

3. DATA ANALYSIS

3.1. General Statistical Methodology

The baseline for each efficacy and safety parameter in a period is defined as the last assessment made on or before the first dose of study drug in that period. That is, baseline for open-label Olanzapine and ALKS 3831 period is defined as the last non-missing observation on or before the first dose of study drug for the open-label period at Visit 2 and 6, respectively; baseline for double-blind period is defined as the last non-missing observation on or before the date of the first dose of study drug for double-blind period at Visit 8.

Unless specified otherwise, the efficacy parameters will be summarized for the double-blind period and the safety parameters will be summarized for the open-label, double-blind and safety follow-up periods.

Continuous variables will be summarized by number of subjects and mean, SD, median, minimum, and maximum values. Categorical variables will be summarized by number and percentage of subjects.

3.2. Definitions of Analysis Populations

3.2.1. Open-label Olanzapine Population

The open-label olanzapine population is defined as all enrolled subjects who received at least 1 dose of olanzapine during the open-label olanzapine treatment period.

3.2.2. Open-label ALKS 3831 Population

The open-label ALKS 3831 population is defined as all enrolled subjects who received at least 1 dose of olanzapine or samidorphan during the open-label ALKS 3831 treatment period.

3.2.3. Safety Population

The safety population is defined as all randomized subjects who receive at least 1 dose of study drug (olanzapine, samidorphan or placebo) during the double-blind placebo-controlled treatment period.

Follow-up safety population is defined as subjects who entered into the follow-up period or have any newly emergent adverse events ([Section 3.8.1](#)).

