9. TREATMENT OF SUBJECTS

9.1. Study Drug Dose and Administration

Study drugs include samidorphan and matching placebo tablets, and olanzapine tablets, all for oral administration.

For all subjects, open-label samidorphan 10 mg will be taken once daily for 2 weeks prior to randomization. For subjects in the double-blind treatment period, samidorphan 10 mg (or placebo) will be taken once daily for up to 15 months.

For all subjects, the dose of olanzapine will be taken once daily (to be taken at the same time as samidorphan/placebo) at an individualized dose level. Olanzapine initiation, including transition from another antipsychotic (as applicable), is a highly individualized process. Formalizing the potential clinical scenarios may pose undue burden and/or risk to subjects. Clinical judgment is essential, and for this reason, the details of this process are left to the discretion of the treating physician, who will follow current clinical practice.

All subjects will be administered olanzapine for 11 to 17 months as part of this clinical trial.

ALKS 3831 should be taken as close to bedtime as possible. Subjects should not drive or operate heavy machinery until they know how ALKS 3831 will affect them.

After Visit 5, the dose level of olanzapine will be fixed, and an increase in dose level above the dose set at Visit 5 prior to randomization may cause the subject to be discontinued. The olanzapine dose level may be decreased at any time if the PI considers it medically beneficial to the subject, such as when a subject has stable psychiatric symptoms with side effects that may be reduced if the olanzapine dose level is decreased. If the PI decreases the dose level after randomization, only an increase above the dose level at randomization will be considered an EEDS.

At study drug dispensation visits, all subjects will receive blister cards containing samidorphan or placebo for self-administration; subjects will also receive olanzapine in separate packaging. Subjects will be instructed to take 1 tablet per day from the blister card in addition to their olanzapine tablet(s) once daily in the evening or at bedtime. The subject will take the final samidorphan/placebo dose the night before the final visit of the double-blind treatment period. Olanzapine dosing will continue uninterrupted through the end of the study. Any subject who prematurely discontinues from the study will be asked to return to the clinic for an ET visit and 2 safety follow-up visits.

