3.8. Safety Analysis

3.8.1. Adverse Events

Adverse events will be coded by System Organ Class and Preferred Term using the Medical Dictionary for Regulatory Activities Version 18.0 (MedDRA®). The verbatim term will be included in the AE listings.

An AE (classified by preferred term) will be considered as treatment-emergent AE (TEAE) if the event is newly occurring or worsening on or after the first dose of study drug.

A TEAE will be summarized for the open-label olanzapine population in the open-label olanzapine period, and for the ALKS 3831 populations in the ALKS 3831 period.

TEAE will be summarized by treatment group for the safety population in the double-blind period. A TEAE will be summarized in the double-blind period if it starts between the date of the

first dose of study drug (inclusive) and the date of the last dose of samidorphan or placebo in the double-blind period.

The number and percentage of subjects reporting TEAEs in each treatment group during the double-blind period will be presented by treatment group and the following categories:

- system organ class and preferred term
- preferred terms in decreasing frequency
- system organ class, preferred term, and severity
- system organ class, preferred term, and relationship
- system organ class, preferred term for drug-related TEAEs

If more than one AE is coded to the same preferred term for the same subject for the same period, the subject will be counted only once for that preferred term using the most severe and most related occurrence for the summarization by severity and by relationship to the study drug.

The incidence of most frequently reported ($\geq 5\%$ of subjects in any treatment group) TEAEs for the double-blind period will be summarized by system organ class, preferred term, and treatment group and will be sorted by decreasing frequency for ALKS 3831 group. It will also be summarized by the olanzapine dose level at randomization.

Newly-emergent AEs (NEAEs), defined as AEs that started or worsened after the date of the last dose of study drug during the treatment period will also be summarized for the follow-up safety population.

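### The SAP's follow-up safety population is partly selected on the outcome, and its AE window need not meet the end of the double-blind TEAE window

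*SAP*

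**What the plan says.** Three SAP rules and two protocol statements bear on this point.

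- **Population.** SAP 3.2.3: "Follow-up safety population is defined as subjects who entered into the follow-up period or have any newly emergent adverse events". SAP 3.8.1 summarizes NEAEs in this population.
- **Start of the NEAE window.** SAP 3.8.1 describes NEAEs as "defined as AEs that started or worsened after the date of the last dose of study drug during the treatment period".
- **End of the double-blind TEAE window.** In the same section, the double-blind TEAE summary takes only events with onset no later than "the date of the last dose of samidorphan or placebo in the double-blind period".
- **Meaning of study drug.** SAP 3.2.3 defines the safety population by receipt of "at least 1 dose of study drug (olanzapine, samidorphan or placebo) during the double-blind placebo-controlled treatment period". Protocol 9.1 agrees: "Study drugs include samidorphan and matching placebo tablets, and olanzapine tablets, all for oral administration".
- **Olanzapine after the blinded tablet stops.** Protocol 9.1: "Olanzapine dosing will continue uninterrupted through the end of the study". Protocol 13.3 has the action taken for an AE recorded separately for olanzapine and for samidorphan/placebo, so the two stop dates can differ.

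**The concern.** There are two separate defects.

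First, part of the denominator is chosen by the outcome. Each subject who did not enter follow-up but joins through the second clause adds one to the numerator and one to the denominator. The corresponding non-entrants without an event are left out. The route is real: Protocol 7.4 requires a telephone attempt, covering safety, when a withdrawn subject does not return.

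Second, the two AE windows are tied to different drugs. TEAEs close on the blinded tablet, and NEAEs open on study drug. Between those dates an AE still meets the SAP's general TEAE definition, which has no end date, but no summary receives it.

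Safety and tolerability are the secondary objective, and the NEAE table describes what happens after treatment ends. A reader would take its percentage as a risk among subjects followed, which it is not.

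The population is also not limited to randomized subjects. The protocol synopsis expects about 450 to start and 270 to be randomized, so about 450 − 270 = 180 may leave earlier. Protocol 7.4 asks subjects who discontinue early to complete safety follow-up. They could enter this denominator without belonging to a randomized arm.

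**Working it through.** The documents give no NEAE rate, no expected share entering follow-up, and no interval between the two stop dates. There is no plan figure to reproduce, and the inputs below are assumptions.

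**1. Denominator.** Let N be all treated subjects, F those who enter follow-up, a those among F with an NEAE, and b the non-entrants with a recorded NEAE.

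- SAP rule: (a + b)/(F + b)
- Entrants only: a/F
- All treated: (a + b)/N

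Since a ≤ F and F + b ≤ N, the SAP figure is never below either alternative. It exceeds a/F only if b > 0 (and a < F).

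**2. Upper bound.** Assume the same true risk q in everyone, a share m not entering, and every non-entrant NEAE recorded. The SAP figure is then q/[(1 − m) + mq]. With q = 10%:

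| Not entering (m) | Calculation | SAP figure |
|---|---|---|
| 10% | 0.10/0.91 | 11.0% |
| 20% | 0.10/0.82 | 12.2% |
| 30% | 0.10/0.73 | 13.7% |
| 40% | 0.10/0.64 | 15.6% |

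**3. Dependence on capture.** With 75% entering and q = 10%, a/N = 0.075 and b/N = c × 0.10 × 0.25, where c is the share of non-entrant NEAEs recorded:

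| c | SAP figure | Entrants only | All treated |
|---|---|---|---|
| 0 | 0.075/0.75 = 10.0% | 10.0% | 7.5% |
| 0.5 | 0.0875/0.7625 = 11.5% | 10.0% | 8.75% |
| 1 | 0.100/0.775 = 12.9% | 10.0% | 10.0% |

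**4. Windows.** An AE is a double-blind TEAE if it starts on or before the last samidorphan/placebo dose. It is an NEAE if it starts after the last study-drug dose, olanzapine included.

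| Last samidorphan/placebo | Last olanzapine in the treatment period | AE starts | Summary |
|---|---|---|---|
| day 100 | day 100 | day 101 | NEAE |
| day 100 | day 107 | day 104 | neither |
| day 100 | day 107 | day 108 | NEAE |

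For completers, Protocol 9.1 puts the final samidorphan/placebo dose on the night before the last double-blind visit. If the treatment period ends at that visit, the gap is about 0 to 1 day. The case that matters is the subject who stops the blinded tablet early and keeps taking olanzapine.

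**5. Net direction.** Take the 75% entry, half-capture case and suppose a share g of post-samidorphan/placebo AEs falls in the gap, for entrants and non-entrants alike. The SAP figure is 0.0875(1 − g)/[0.75 + 0.0125(1 − g)]. For g = 0, 10%, 25% and 50% it is 11.5%, 10.3%, 8.6% and 5.8%, against a true 10%.

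Unequal risk can also reverse the sign with no gap at all. With 10% risk in entrants, 30% in non-entrants and half of the latter captured, the SAP figure is (0.075 + 0.0375)/(0.75 + 0.0375) = 14.3%. The true risk is 0.075 + 0.075 = 15.0%.

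**The case against.** The strongest reply is that both defects are small and the second may be only loose wording. If study drug in the NEAE definition means the blinded tablet, the windows meet exactly, and SAP 6.1 does tie its last-dose rule to samidorphan/placebo. The non-entrants are also the subjects hardest to observe, so few of their events may be recorded. Listings retain every AE, SAEs are listed for the whole study, and AEs leading to discontinuation have their own summary.

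Much of this stands, and it limits the size. It does not remove the point. SAP 3.2.3 itself spells out that study drug includes olanzapine. Where the SAP means the blinded tablet it generally says so, as in the TEAE sentence of 3.8.1 and the double-blind qualifier in 3.7.3.1.2 and 3.7.4.6.3. Even on the kinder reading, one term carries two meanings. The outcome clause needs no interpretation.

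Several stronger inferences are tempting but unsupported:

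- *The plan treats gap days as on-treatment elsewhere.* The 7-day rule in SAP 6.1 maps early-termination assessments to analysis visits. It is not an AE window, so it does not conflict with 3.8.1.
- *This table is the trial's only evidence on stopping samidorphan.* All subjects take open-label samidorphan for two weeks and half are then randomized to placebo. The double-blind TEAE table therefore also compares stopping with continuing.
- *Gap days hold the events that made subjects stop.* Such an event would normally begin on or before the last dose, inside the TEAE window.
- *The rule creates a false difference between arms.* SAP 3.8.1 does not say that NEAEs are summarized by arm.

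**Conclusion.** Both defects follow from the SAP's own wording. The population rule can inflate the NEAE percentage relative to an entrants-only or all-treated denominator. At a 10% risk shared by all subjects, with 10% to 40% not entering, the ceiling is 11.0% to 15.6%. The excess over the entrants-only rate therefore runs from zero to about 5.6 percentage points, depending on how many non-entrant events are recorded.

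The window rule can omit from both summaries AEs that start after an early stop of samidorphan/placebo while olanzapine continues in the treatment period. This rests on study drug including olanzapine, as the documents define it. The number of such events cannot be derived.

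A reader might infer that post-treatment AE rates will be overstated. The documents do not support that: lost gap events pull the figure down, and so does incomplete capture among higher-risk non-entrants. The net sign against the true risk is unknown. The table is descriptive, no test depends on it, and the efficacy analyses are untouched. The point is worth correcting because the rules are plainly stated and cheap to repair.

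**What to change.** **SAP 3.2.3.** Delete the clause that admits subjects because they have an NEAE. Define the follow-up safety population as safety-population subjects who entered the follow-up period, or alternatively as all safety-population subjects. Of the two, the entrants-only version avoids counting unobserved subjects as event-free, which is why the all-treated figure falls to 7.5% when nothing is captured in the working above. It describes only those followed, and the table should say so. Do not use telephone or ad hoc contact as an entry route, because a contact prompted by an AE would bring the selection back. List NEAEs reported outside the population, and tabulate subjects who left before randomization separately.

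**SAP 3.8.1.** For randomized subjects, start the NEAE window on the day after the last samidorphan/placebo dose, naming those tablets instead of study drug, so that it meets the TEAE window exactly.

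The cost is two revised SAP sentences and a programming change. No new data are needed.

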3.2.4. Efficacy Population

The intent-to-treat (ITT) population is the same as the safety population.

3.3. Disposition

The number and percentage of subjects completing or prematurely discontinuing during the open-label olanzapine period and the open-label ALKS 3831 period will be summarized. For the safety population, the number and percentage of subjects completing or prematurely

discontinuing the study and reason for discontinuation will be summarized by treatment group; and overall.

3.4. Demographics and Baseline Characteristics

Demographics and baseline characteristics, including but not limited to, sex, age, race, ethnicity, region, weight, BMI, PANSS, CGI-S and drinking status will be summarized for the open-label populations and by treatment group and overall for the safety population.

Assignment of the stage of readiness to change will be based on the quick method³. The scale score is the sum of the item scores. The highest scale score represents the stage of change designation. The score of the precontemplation scale is reversed to compare with the contemplation and action scales. If two scale scores are equal, the scale farther along the continuum of change (ie precontemplation - contemplation - action) represents the subject's stage of change designation.

Medical history will be summarized for the open-label olanzapine population (overall) and for the safety population (by treatment group and overall).

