8.3.9. Readiness to Change Questionnaire

The Readiness to Change Questionnaire ([Appendix B](#)) [[Rollnick, 1992](#)] is a self-report measure that will be administered at screening.

The Readiness to Change Questionnaire is included as an exploratory measure that may be useful as a potential predictor of efficacy or stratification factor for assessing efficacy in sub-groups.

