APPENDIX B. SAMPLE READINESS TO CHANGE QUESTIONNAIRE

SAMPLE READINESS TO CHANGE QUESTIONNAIRE

0=strongly agree; 1=agree; 2=unsure; 3=disagree; 4=strongly disagree

- | | | | | | |
|---|---|---|---|---|---|
| 1. I don't think I drink too much | 0 | 1 | 2 | 3 | 4 |
| 2. I am trying to drink less than I used to | 0 | 1 | 2 | 3 | 4 |
| 3. I enjoy my drinking, but sometimes I drink too much | 0 | 1 | 2 | 3 | 4 |
| 4. Sometimes I think I should cut down on my drinking | 0 | 1 | 2 | 3 | 4 |
| 5. It's a waste of time thinking about my drinking | 0 | 1 | 2 | 3 | 4 |
| 6. I have just recently changed my drinking habits | 0 | 1 | 2 | 3 | 4 |
| 7. Anyone can talk about wanting to do something about drinking, but I am actually doing something about it | 0 | 1 | 2 | 3 | 4 |
| 8. I am at the stage where I should think about drinking alcohol less | 0 | 1 | 2 | 3 | 4 |
| 9. My drinking is a problem sometimes | 0 | 1 | 2 | 3 | 4 |
| 10. There is no need for me to think about changing my drinking | 0 | 1 | 2 | 3 | 4 |
| 11. I am actually changing my drinking habits right now | 0 | 1 | 2 | 3 | 4 |
| 12. Drinking less alcohol would be pointless for me | 0 | 1 | 2 | 3 | 4 |

**APPENDIX C. SAMPLE POSITIVE AND NEGATIVE SYNDROME
SCALE**

SCI-PANSS

SCI-PANSS

Structured Clinical Interview – Positive and Negative Syndrome Scale

[name]., Ph.D.
[name].
J.P. Lindenmayer, M.D., &
[name].

SAMPLE

Structured Clinical Interview for the Positive and Negative Syndrome Scale

SCI-PANSS

L. A. Opler, M.D., Ph.D. S. R. Kay, Ph.D. J. P. Lindenmayer, M.D. A. Fiszbein, M.D.

Patient Name or ID: _____

Interviewer: _____ Date: ____ / ____ / ____

Data on "Lack of Spontaneity and Flow of Conversation" (N6),
"Poor Rapport" (N3), and "Conceptual Disorganization" (P2)

Hi, I'm ... We're going to be spending the next 30 to 40 minutes talking about you and your reasons for being here. Maybe you can start out by telling me something about yourself and your background?

(Instruction to interviewer: Allow at least 5 minutes for a non-directive phase serving to establish rapport in the context of an overview before proceeding to the specific questions listed below.)

Data on "Anxiety" (G2)

1. Have you been feeling worried or nervous in the past week? _____
IF YES, skip to question 3. IF NO, continue.
2. Would you say that you're usually calm and relaxed? _____
IF YES, skip to question 8. IF NO, continue.
3. What's been making you feel nervous (worried, not calm, not relaxed)? _____

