3.7.2.1. Primary Analysis of the Primary Efficacy Endpoint

For the primary analysis of time to the first EEDS, comparison of the 2 treatment groups will be carried out using a log rank test. The Cox proportional hazards model will be used to obtain an estimate of the hazard ratio for the ALKS 3831 group to the olanzapine group adjusting for the baseline PANSS total score and drinking status. A 95% confidence interval will be computed for the hazard ratio.

Kaplan-Meier estimates of EEDS rate will be generated and the Kaplan-Meier plot of time to first EEDS will be presented by the treatment group.

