6. DEFINITIONS AND CONVENTIONS FOR HANDLING OF THE DATA

Dataset specifications will be provided in a separate document.

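### SAP 3.4's readiness-to-change scoring does not fit the Appendix B item coding: all three scores rise with denial, so the highest one does not identify the stage the subject endorses

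*SAP*

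**What the plan says.** SAP 3.4 says stage will follow the quick method, citing the questionnaire's user's manual, and then writes the algorithm out:

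- Scoring: "The scale score is the sum of the item scores".
- Assignment and reversal: "The highest scale score represents the stage of change designation. The score of the precontemplation scale is reversed", the stated purpose being comparison with the contemplation and action scales.
- Ties: "If two scale scores are equal, the scale farther along the continuum of change" gives the designation, the order being precontemplation, contemplation, action.

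The only item coding in either document is the single key printed above all 12 items in Protocol Appendix B: "0=strongly agree; 1=agree; 2=unsure; 3=disagree; 4=strongly disagree".

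The SAP gives neither the stored item coding nor the assignment of items to scales. SAP section 6 says "Dataset specifications will be provided in a separate document". Protocol 8.3.9 describes the questionnaire as exploratory and says it "may be useful as a potential predictor of efficacy or stratification factor for assessing efficacy in sub-groups".

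**The concern.** A highest-score rule works only if a high score means the same thing on every scale, namely agreement with that stage's statements. Under the Appendix B key a high raw sum means disagreement on all three scales. Reversing precontemplation alone makes it the only scale on which high means agreement. Because agreeing with precontemplation statements is itself denial, all three scores now increase as the subject denies a drinking problem. Between contemplation and action, the maximum picks the one the subject endorses less.

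At stake is the reported baseline distribution of stage, together with any later predictor or subgroup analysis of the kind Protocol 8.3.9 allows for. A swapped contemplation/action label would mislead such an analysis without any visible sign.

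**Working it through.** The plan states no figure that depends on this rule, so there is none to reproduce. The check applies the rule as printed.

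**Inputs.** Item values 0 to 4 come from Appendix B. The sum, reversal, maximum and tie rules come from SAP 3.4. Two assumptions are added. First, four items per scale are assigned from their wording, because no key is printed: precontemplation (P) 1, 5, 10, 12; contemplation (C) 3, 4, 8, 9; action (A) 2, 6, 7, 11. Second, the two-way tie rule is extended to three-way ties.

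**Formula.** P score = 16 − raw P sum; C score = raw C sum; A score = raw A sum. The maximum wins and ties go to the later stage.

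**Single subjects, Appendix B coding**

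| Answers to P / C / A items | Scores P/C/A | SAP label |
|---|---|---|
| disagree / agree / disagree | 4/4/12 | Action |
| strongly disagree / agree / strongly agree | 0/4/0 | Contemplation |
| agree / disagree / disagree | 12/12/12 | Action, by tie |
| strongly agree / strongly disagree / strongly disagree | 16/16/16 | Action, by tie |
| strongly agree / disagree / disagree | 16/12/12 | Precontemplation (correct) |

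**Enumeration, Appendix B coding.** For each profile, let every item take one of its two agree options or one of its two disagree options with equal weight (2^12 = 4,096 patterns). Each scale then covers a five-point range with weights 1, 4, 6, 4, 1 (out of 16) and cumulative weights 1, 5, 11, 15, 16.

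- *Contemplation-only:* P and C scores lie in 0–4 and A in 12–16, so 100% are labelled Action.
- *Action-only:* P and A lie in 0–4 and C in 12–16, so 100% are labelled Contemplation.
- *Denier:* all three lie in 12–16 with the same distribution.
  - Precontemplation needs P strictly above both others: (4×1² + 6×5² + 4×11² + 1×15²)/4,096 = 863/4,096 = 21.1%.
  - Action needs A at least equal to both: (1×1² + 4×5² + 6×11² + 4×15² + 1×16²)/4,096 = 1,983/4,096 = 48.4%.
  - Contemplation is the remainder: 1,250/4,096 = 30.5%.
  - Misclassified: 48.4% + 30.5% = 78.9%. Three-way ties make up (1 + 64 + 216 + 64 + 1)/4,096 = 8.4% of patterns, all counted as Action.

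**Same rule, all items stored with agreement high.**

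- *Denier:* all three scores lie in 0–4, so the split is the same and 78.9% are wrong.
- *Contemplation-only:* P and C both lie in 12–16. C is at least P in (1×1 + 4×5 + 6×11 + 4×15 + 1×16)/256 = 163/256 = 63.7%. The other 36.3% are labelled Precontemplation.
- *Action-only:* the same, 63.7% correct and 36.3% Precontemplation.
- Example: a subject who strongly rejects precontemplation and agrees with everything else scores 16/12/12 and is labelled Precontemplation.

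**A different weighting.** Take all 5^12 = 244,140,625 patterns (unsure included) as equally likely, and define the endorsed stage as the scale with most agreement under the same tie rule. On Appendix B coding the SAP label matches in 16.7% overall: 45.8% of patterns endorsing precontemplation, 0% of those endorsing contemplation and 9.2% of those endorsing action. On agree-high coding the overall match is 54.7%.

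**After correction.** With agreement high on every scale, the endorsed scale lies in 12–16 and the other two in 0–4, so all three profiles are classified correctly in 100% of patterns.

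**The case against.** The best defence is that the operative method sits elsewhere. The SAP cites a manual, leaves dataset specifications to another document, and Appendix B is labelled a sample. If precontemplation items were stored with agreement low and the other eight with agreement high, reversing precontemplation alone would align the scales and the rule would work. That is logically right. However, nothing in either document describes mixed storage, and Appendix B prints one key for all items. Nor does the unseen manual repair an algorithm the SAP spells out: if the manual's method differs, the SAP paragraph misstates it.

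It can also be said that the percentages depend on idealised profiles, inferred item membership and an added three-way tie rule. This stands. The two weightings give different figures (21.1% against 45.8% correct for precontemplation), so the numbers show the direction of the fault and do not forecast the error rate among subjects.

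Finally, stage drives nothing confirmatory. The primary Cox model is fitted "adjusting for the baseline PANSS total score and drinking status", stage is not among the eight subgroups in SAP 3.7.2.4, and it is not an efficacy endpoint. This also stands and limits the importance of the point.

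**Conclusion.** The concern holds. Applied to the only item coding in the documents, the SAP 3.4 rule mislabels clear-cut contemplation and action responders and most of the enumerated denial patterns. It also fails if all items are stored with agreement high. The conclusion about direction rests on the printed texts and on item membership read from the wording; the percentages rest further on equal weights and the extended tie rule. The primary result and every planned efficacy model are unaffected. The baseline stage table, and any exploratory analysis by stage, would be wrong. This should be corrected, but it does not threaten the trial's main conclusions.

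**What to change.** In SAP 3.4:

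1. State the stored item coding and list the items in each scale, checked against the cited manual.
2. Score all three scales so that high means agreement. If items are stored as in Appendix B, use 4 minus the value for all 12; if they are stored with agreement high, no recode is needed.
3. Delete the separate reversal of precontemplation. Settle step 1 first: should the precontemplation items alone prove to be stored in the opposite direction, the recode belongs to those items only.
4. Assign the stage with the highest sum, and say explicitly that two-way and three-way ties go to the later stage.

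The cost is one SAP paragraph and the derivation code. Item responses are already collected, so no new data are needed.
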